3.4.2 Safety Endpoints

Safety measurements are as described in Section 4.2.3.2 of the protocol.

The primary safety endpoints are AEs graded using CTCAE (Version 4.0 or above) criteria. Safety will be assessed by quantifying the toxicities and grades experienced by subjects who have received pembrolizumab, including serious adverse events (SAEs) and events of clinical interest (ECIs). Other safety endpoints include laboratory safety assessments, vital signs, reasons for treatment discontinuation, dose interruptions or reductions, and physical examinations.

3.5 Analysis Populations

3.5.1 Efficacy Analysis Populations

Cohort A

The all subjects as treated (ASaT) in Cohort A who receive at least one dose of study treatment, will serve as the primary population for the analyses of efficacy data for Cohort A *All Comers*. The all subjects as treated (ASaT) population for PD-L1_H subgroup in Cohort A, which includes the subjects in the confirmation set above the PD-L1 cut-off, will be used for the analyses of efficacy data for PD-L1_H subjects in Cohort A

Cohort B

The all subjects as treated (ASaT) population consists of all subjects in Cohort B who receive at least one dose of study treatment. The all subjects as treated (ASaT) population for PD-L1_H subgroup in Cohort B, which includes the subjects in Cohort B above the PD-L1 cut-off, will be used for the analyses of efficacy data for PD-L1_H subjects in Cohort B.

3.5.2 Safety Analysis Populations

The all subjects as treated (ASaT) population will be used for the analysis of safety data. At least one laboratory or vital sign measurement obtained subsequent to at least one dose of study treatment is required for inclusion in the analysis of each specific parameter. To assess change from baseline, a baseline measurement is also required.

3.6 Statistical Methods

3.6.1 Statistical Methods for Efficacy Analyses

This section describes the statistical methods that address the primary and secondary objectives.

Data from the training set (first 100 subjects in Cohort A) will be evaluated for biomarker analysis and cut point determination. Subjects who did not meet Treatment-free Interval/Platinum-free Interval inclusion criteria for Cohort A would be excluded from the cut point determination analysis.

Efficacy will be evaluated in the *All Comer* group and the PD-L1_H subgroup for Cohort A and B respectively. For the primary efficacy endpoint, the ORR based on RECIST 1.1 by the BICR, the point estimate, and 95% confidence interval (as determined by the upper and lower 97.5% one-sided confidence bounds) will be provided using an exact binomial distribution. Secondary efficacy evaluations of ORR based on RECIST 1.1 by investigator review, DCR based on RECIST 1.1 by the BICR and ORR based on irRECIST by BICR will also be conducted using the same methodology as for the primary efficacy analysis. Subjects without response data will be counted as non-responders and disease not controlled.

Duration of response by BICR and investigator review will be summarized using Kaplan-Meier method in all responders.

For PFS and OS, Kaplan-Meier (KM) curves, median estimates, and survival at 6, 12 and 18 months based on the KM curves (95% CI is based on Greenwood's formula) will be provided as appropriate. Subjects without efficacy evaluation data or without survival data will be censored at Day 1. The restricted Mean Survival Time estimate of PFS and OS will also be calculated and plotted over time. Censoring rules for DOR and PFS are summarized in [Table 1](#) and [Table 2](#) respectively.

Table 1 Censoring Rules for Analyses of DOR

Situation	Date of progression or censoring	Outcome
No progression nor death, no new anti-cancer therapy initiated	Last adequate assessment	Censor (non-event)
No progression nor death, new anti-cancer therapy initiated	Last adequate assessment before new anti-cancer therapy initiated	Censor (non-event)
Death or progression after ≥ 2 consecutive missed adequate disease assessments	Last adequate assessment prior to ≥ 2 missed adequate disease assessments	Censor (non-event)
Death or progression after ≤ 1 missed adequate disease assessments	Death or progression	End of response (Event)
A missed disease assessment includes any assessment that is not obtained or is considered inadequate for evaluation of response.		

Table 2 Censoring Rules for Analyses of PFS

Situation	Date of progression or censoring
No PD and no death; new anticancer treatment is not initiated	Censored at last disease assessment
No PD and no death; new anticancer treatment is initiated	Censored at last disease assessment before new anticancer treatment
PD or death documented after ≤ 1 missed disease assessment	Progressed at date of documented PD or death
PD or death documented after ≥ 2 missed disease assessments	Progressed at date of documented PD or death

An outline of the key efficacy analysis strategy is presented in [Table 3](#).

Table 3 Analysis Strategy for Key Efficacy Endpoints

Endpoint	Statistical Method	Analysis Population	Missing Data Approach

 • ORR by BICR per RECIST1.1 • ORR by investigator assessment per RECIST1.1 	Exact test of binomial parameter; 95% CI [†]	ASaT	Subjects with missing data are considered non-responders

 • DOR by BICR per RECIST1.1 • DOR by investigator assessment per RECIST1.1 	Summary statistics using Kaplan-Meier method	All responders	Refer to Table 1

 • PFS by BICR and investigator assessment per RECIST 1.1 	Summary statistics using Kaplan-Meier method	ASaT	Refer to Table 2

 • DCR by BICR and investigator assessment per RECIST 1.1 	Exact test of binomial parameter; 95% CI [†]	ASaT	Subjects with missing data are considered disease not controlled

 • OS 	Summary statistics using Kaplan-Meier method	ASaT	Censored at last known alive date
[†] 95% confidence interval is determined by the upper and lower 97.5% one-sided confidence bounds.			

The strategy to address multiplicity issues with regard to multiple endpoints and interim analyses is described in Section 3.7, Interim Analyses and in Section 3.8, Multiplicity.

The evaluation of a general positive association between CPS and BOR will be investigated via standard logistic regression as well as generalized additive models. The potential for a cut-off greater than CPS 1% to define a PD-L1 positive population with good clinical utility will depend on the strength of evidence in the observed association, as well as a detailed evaluation of the relative improvement in clinical utility with higher cut-offs. This evaluation involves a review of the positive predictive value (PPV, response rate in those above a cut-off), sensitivity (proportion

above the cutoff among responders), negative predictive value (NPV, non-response rate in those below the cut-off), specificity (proportion below the cutoff among non-responders), and fraction of PD-L1 positive patients (prevalence) as functions of increasing cut-offs. A clinically useful PD-L1 positive cut-off should maintain high NPV (e.g. near or above 90%) while achieving a meaningful enrichment of response, and largely capturing patients showing durable clinical benefit is sought. A receiver operating characteristic curve, and graphical illustrations will be utilized to assess the performance of a binary classifier and to understand the sensitivity and specificity profile in the context of PPV and NPV. Analyses will also be performed on PFS and OS, as appropriate, examining associations using cox proportional hazards models and KM estimates with graphical illustrations. CPS ranges for any promising cut-offs will also have to be gauged in the context of practical implementation and interpretation by pathologists in clinical practice.

The associations between clinical response and other biomarkers, e.g., immune-related mRNA expression signatures and somatic mutational load, will be evaluated similarly.

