7.1.2.6.4 End of Treatment and Follow-up Tumor Imaging

In subjects who discontinue trial treatment without documented disease progression, every effort should be made to continue monitoring their disease status by tumor imaging using the same imaging schedule used while on treatment (Q9W (63 days \pm 7 days) from the date of allocation up to 54 weeks with subsequent imaging performed Q12W (84 days \pm 7 days).) to monitor disease status until (1) the start of new anti-cancer treatment, (2) disease progression, (3) death, or (4) the end of the study, whichever occurs first.

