3.4.1 Efficacy Endpoints

Primary

- **Objective response rate (ORR) - per RECIST 1.1 assessed by BICR**

Objective Response Rate (ORR), defined as the proportion of subjects in the analysis population who have confirmed complete response (CR) or partial response (PR) at any time during the study.

Secondary

- **Duration of Response (DOR) - per RECIST 1.1 assessed by BICR and by investigator**

Duration of response (DOR), defined as the time from first documented evidence of response to disease progression in subjects who achieve a confirmed PR or CR.

- **Progression-free Survival (PFS) - per RECIST 1.1 assessed by BICR and by investigator**

Progression-free survival (PFS), defined as the time from the first day of study treatment to the first documented disease progression or death due to any cause, whichever occurs first.

- **Overall survival (OS)**

Overall survival (OS), defined as the time from the first day of study treatment to death due to any cause.

- **Disease Control Rate (DCR) - per RECIST 1.1 assessed by BICR**

Disease Control Rate (DCR), defined as the percentage of subjects who have achieved confirmed CR or PR or have demonstrated SD for at least 24 weeks prior to any evidence of progression.

Exploratory

- **Progression-free survival (PFS) – irRECIST assessed by BICR**

Progression-free-survival (PFS) is defined as the time from first day of study treatment to the first confirmed disease progression or death due to any cause, whichever occurs first.

ORR and DOR per irRECIST by BICR are also the exploratory efficacy endpoints.

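### sSAP Table 2 censors a subject who switches therapy only while she is alive at the data cut, so PFS estimates can drift upward as follow-up lengthens

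*Combined protocol and SAP*

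**What the plan says.** sSAP section 3.6.1, Table 2, has four rows for PFS. Two cover subjects with neither progression nor death. The one for new therapy reads "No PD and no death; new anticancer treatment is initiated", with the action "Censored at last disease assessment before new anticancer treatment". The other two are "PD or death documented after ≤ 1 missed disease assessment" and "PD or death documented after ≥ 2 missed disease assessments". Both lead to "Progressed at date of documented PD or death", and neither mentions new therapy.

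sSAP section 3.4.1 gives PFS as "defined as the time from the first day of study treatment to the first documented disease progression or death due to any cause", with no exclusion of events after a switch. Protocol Table 8 has only a general instruction to censor PFS at the last assessment. No PFS sensitivity analysis is planned.

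Protocol section 7.1.2.6.4 has subjects who stop treatment without progression scanned "to monitor disease status until (1) the start of new anti-cancer treatment, (2) disease progression, (3) death". Section 7.1.2.6.2 likewise ends imaging at new therapy. Section 7.1.5.3.4 keeps such subjects under telephone contact for survival about every 12 weeks.

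**The concern.** After a switch, deaths are recorded but progressions mostly are not. Take two subjects who switch at month 4 without documented progression. The one alive at the cut leaves the risk set at her last scan before month 4. The one who dies at month 20 stays in it, as progression-free, until month 20. A later outcome decides how long each was at risk, which breaks the independent-censoring assumption of Kaplan-Meier.

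For PFS by central review, the likely route is progression called by the site, then new therapy, with no progression on central reading. Treatment decisions follow the site (protocol 2.1.2 and 7.1.2.6.7). For investigator PFS, it is a switch on clinical decline without radiographic progression.

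At stake are the PFS curve and the 6-, 12- and 18-month PFS rates named in protocol section 3.2. Durability is part of the trial's rationale (section 4.2.3.1), so an artefact that lifts late PFS matters.

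**Working it through.** The documents give no expected PFS, event count or switch share, so there is no plan figure to reproduce. Three checks were made.

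**1. Direction.** Kaplan-Meier is S(t) = product of (1 - d_j/n_j) over event times up to t. Choose a t that every subject has been followed past at the earlier cut. A switcher alive then is censored before t. If she has died by the later cut, she becomes an event after t. She joins earlier risk sets (n_j rises) and adds no event before t (d_j is unchanged). No factor falls, so S(t) rises or stays the same.

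**2. Ten-subject example, 6-month PFS.** All enter at time 0. Two progress at month 2 and two at month 4. Six switch at month 3 (last scan month 2) and die at months 5, 8.5, 14, 18.5, 24 and 30. The factor at month 2 is 8/10 in every row.

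| Data cut (month) | Switchers dead | Factor at month 4 | Factor at month 5 | 6-month PFS |
|---|---|---|---|---|
| 8 | 1 | 1/3 | 0/1 | 0% |
| 12 | 2 | 2/4 | 1/2 | 20% |
| 20 | 4 | 4/6 | 3/4 | 40% |
| 36 | 6 | 6/8 | 5/6 | 50% |

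Nothing that happened before month 6 differs between rows.

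**3. Simulation.**

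Inputs from the documents:
- Accrual: 48 - 36 = 12 months (Trial Summary; section 2.1.1).
- Cuts: 12 + 8 = 20 months (response-rate cut) and 12 + 36 = 48 months (final OS cut), from first enrolment.
- Scans every 9 weeks to week 54, then every 12.
- Median time to progression 3.4 months and median OS 12 months, borrowed from the chemotherapy figures in section 4.1.1.1. Survival after progression is then 12 - 3.4 = 8.6 months.

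Assumed: share switching without documented progression 5%, 10% or 20%; a shorter alternative of 3 months for post-progression survival; exponential times; uniform accrual; switch at the moment of underlying progression; the same residual survival for all. There were 400,000 subjects per scenario. Rule (a) always censors at the last pre-switch scan. Rule (b) never censors at the switch, counts later deaths, and censors the living at last known alive date.

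12-month PFS (%), 20-month cut to 48-month cut:

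| Share | Post-switch median | Table 2 as written | Drift | Rule (a) | Rule (b) |
|---|---|---|---|---|---|
| 5% | 3 | 11.6 to 12.2 | 0.6 | 12.3 to 12.5 | 11.9 to 12.2 |
| 5% | 8.6 | 12.6 to 14.0 | 1.4 | 12.9 to 13.0 | 14.0 to 14.1 |
| 10% | 3 | 12.0 to 13.0 | 1.0 | 13.5 to 13.7 | 12.7 to 13.0 |
| 10% | 8.6 | 13.5 to 16.2 | 2.7 | 14.1 to 14.2 | 16.3 to 16.5 |
| 20% | 3 | 12.7 to 14.6 | 1.9 | 16.4 to 16.6 | 14.2 to 14.6 |
| 20% | 8.6 | 15.3 to 20.5 | 5.2 | 17.1 to 17.1 | 20.8 to 21.0 |

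As written, the estimate starts below both rules and slides towards (b) as deaths accrue. Rules (a) and (b) move by at most 0.2 and 0.4 points. As-written 6-month PFS rises by 0.1 to 1.8 points over the same scenarios. At 18 months the extremes are 2.1 to 2.9% (5%, 3 months) and 2.4 to 8.7% (20%, 8.6 months).

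A second model, with median time to progression 4 months and 10-month post-switch survival, agrees. Its 12-month PFS goes from 13.8 to 17.1% at about 11% switching and from 12.9 to 19.7% at about 23%. Its median PFS stays at 4.1 months at about 11% and moves from 4.1 to 4.4 at about 23%.

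**The case against.** The strongest reply is that PFS is secondary, single-arm and untested, and that the size rests on a switch share the documents do not give. That stands. At 15% PFS the sampling half-width is 1.96 x sqrt(0.15 x 0.85/250) = 4.4 points for n = 250 and 8.1 for n = 75, so at low shares the drift is well inside sampling error. The protocol also does not say that PFS will be reported at both cuts. But a rule whose answer depends on the cut remains a defect, and it is cheap to remove.

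It could also be said that counting deaths after a switch is a treatment-policy choice. That fails: such a policy would not censor the living at the switch, and Table 2 does.

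Four stronger readings are tempting and not supported:
- *That Table 1 (DOR) has the same fault.* Its row "No progression nor death, new anti-cancer therapy initiated" is built alike, but Table 1 also censors death or progression after two or more consecutive missed assessments. As imaging ends at the switch, most later deaths are already censored.
- *That a 12-month rate already fully observed will rise.* At the response-rate cut the last subject may have only 8 months of follow-up. The algebra covers 6 months; 12 and 18 months rest on simulation.
- *That always censoring makes late PFS less favourable.* With 20% switching and 3-month post-switch survival it gives 16.6%, against 14.6% as written, at the 48-month cut.
- *That switching on CA-125 is a main route.* Protocol section 2.1.2 bars its use for determining progression.

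**Conclusion.** The concern holds for PFS. Read literally, Table 2 makes censoring after new therapy depend on later vital status, and no other text supplies a different rule. The table never names the case of new therapy followed by progression or death, so the sponsor may intend something else and should say so.

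Under the stated assumptions, 12-month PFS drifts up by about 0.6 to 5 points between the 20- and 48-month cuts. The 6-month rate moves less, and the median barely moves at low shares. The primary response rate is unaffected. This should be corrected, but it does not threaten the trial's main conclusion.

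**What to change.** In Table 2, apply one rule to every subject who starts new therapy without documented progression, chosen by the sponsor before the PFS data are reviewed:

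- **(a)** censor at the last disease assessment before new therapy, whatever follows; or
- **(b)** do not censor at new therapy: count all later progressions and deaths, and censor the living at the last known alive date.

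Report the other rule, and new therapy counted as a PFS event, as sensitivity analyses, with the number of subjects concerned. Table 1 needs at most a clarifying condition.

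The cost is a few reworded rows and two extra runs, with no new data. Neither rule is neutral. Rule (a) loses events, possibly many if switching is common, and is informative if switching follows clinical decline. Rule (b) fits the any-cause-death definition but treats switchers as progression-free until death. Reported PFS may move either way. Rule (a) also leaves a similar look-back for subjects who stop imaging without new therapy (alive: last scan; dead: event at death), so the intended handling of that case should be stated too.

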3.6.2 Statistical Methods for Safety Analyses

Safety and tolerability will be assessed by clinical review of all relevant parameters including adverse experiences (AEs), laboratory tests, and vital signs. Summary statistics (counts, percentage, mean, standard deviation, etc.) will be provided for the safety endpoints as appropriate.

3.6.3 Demographic and Baseline Characteristics

Baseline characteristics will be assessed by the use of tables and/or graphs. No statistical hypothesis tests will be performed on these characteristics. The number and percentage of subjects screened, enrolled, primary reasons for screening failure, and discontinuation will be displayed. Demographic variables (e.g., age, gender), baseline characteristics, primary and secondary diagnoses, and prior and concomitant therapies will be summarized either by descriptive statistics or categorical tables. The *All Comer* group and the PD-L1_H subgroup will be summarized separately for Cohort A and Cohort B.

3.7 Interim Analysis

An interim analysis will be performed after 100 subjects in Cohort A have been enrolled and followed up for at least 4 months to determine a PD-L1 expression cutpoint based on PD-L1 biomarker and tumor response data. The results of this analysis will be presented to the study team without unblinding anyone to biomarker results for any individuals. The efficacy data from the interim analysis may facilitate further interactions with regulatory agencies.

3.8 Multiplicity

The primary objectives for ORR per RECIST 1.1 in All Comer Population and PD-L1_H subgroup for Cohort A and Cohort B will be assessed by point estimate and 95% confidence interval. There are no formal hypotheses and no adjustments for multiplicity are planned. Evaluation of objectives should be interpreted with caution due to the potential for an increase in the false positive rate.

3.9 Sample Size and Power Calculations

Based on the preliminary data of pembrolizumab in ovarian cancer patients as described in Section 4.1.2 of the protocol, we expect an ORR of approximately 25% for the *All Comer* population. These responding subjects expect to have durable responses. In addition we expect additional subjects will have durable stable disease. We expect in a PD-L1 enriched population, ORR may reach to above 35% with durable response in majority of the subjects.

Table 4 shows the two-sided 95% confidence interval of ORR for different observed response rates based on different sample size in the *All Comer* group for Cohort A or Cohort B.

Table 4 Two-sided 95% Confidence Interval of ORR in All Comer

Sample Size	Observed ORR	95% CI of ORR (%)
75	17%	(9.3, 27.4)
	25%	(15.7, 36.3)
	30%	(20.0, 41.7)
	35%	(24.3, 46.9)
100	17%	(10.2, 25.8)
	25%	(16.9, 34.7)
	30%	(21.2, 40.0)
	35%	(25.7, 45.2)
180	17%	(12.0, 23.5)
	25%	(18.9, 32.0)
	30%	(23.4, 37.3)
	35%	(28.1, 42.4)
250	17%	(12.7, 22.5)
	25%	(20.0, 31.1)
	30%	(24.4, 36.1)
	35%	(29.3, 41.5)

For the PD-L1_H subgroup, if the prevalence of PD-L1_H is about 40%, there will be approximately 60 PD-L1_H subjects if there are 150 all comer subjects in the confirmation set, and approximately 30 PD-L1_H subjects if there are 75 all comer subjects in Cohort B. Table 5 shows the two-sided 95% CI of ORR with 30 and 60 subjects for different response rates.

The sample size for the training set (n=100), was selected to achieve adequate precision on the PPV and NPV profiles as a function of putative cut-offs.

Table 5 Two-sided 95% Confidence Interval for ORR in PD-L1_H

Sample Size	Observed ORR	95% CI of ORR (%)
30	25%	(12.2, 45.9)
	30%	(14.7, 49.4)
	35%	(17.3, 52.8)
	40%	(22.7, 59.4)
60	25%	(14.7, 37.9)
	30%	(18.9, 43.2)
	35%	(23.1, 48.4)
	40%	(27.6, 53.5)

3.10 Subgroup Analyses and Effect of Baseline Factors

The estimate of the treatment effect for the primary endpoint will be estimated and/or plotted within each category of the following classification variables:

- Age category (<65 , ≥65 years)
- Race (Asian , non-Asian)
- Platinum sensitivity (platinum resistant recurrent, partial platinum sensitive recurrent)
- ECOG Performance Status (0,1)
- Histology (high-grade serous, mucinous, endometrioid, clear cell, and other)

3.11 Extent of Exposure

The extent of exposure will be summarized as number of cycles in which the subject receives the study medication infusion.
